### *Specific Considerations in COVID-19*

There is potentially a slight elevation in the risk of thrombosis with standard IVIG therapy, and in some cases COVID-19 is associated with thrombotic complications. Hence participants with pre-existing prothrombotic tendencies will not be included and any thrombotic events will form part of the primary endpoint assessment and be monitored during interim safety analyses by the DSMB.

There is a theoretical risk the antibody infusion may worsen the disease course of COVID-19 via antigen-dependent enhancement (ADE). It is unclear if this phenomenon is relevant and clinically significant in COVID-19, but to ensure detection of any such phenomenon (which could be manifested by disease progression soon after hIVIG infusion) close monitoring of clinical disease outcomes will be maintained in the randomized groups, including in the days prior to the primary endpoint assessment at Day 7.

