# **4 OBJECTIVES AND ENDPOINTS**

## **4.1 Primary Objectives and Primary Endpoint**

The primary objective is to compare the clinical status of participants in the hIVIG + SOC and placebo + SOC groups on Day 7 using an ordinal outcome with 7 mutually

exclusive categories. On Day 7, the worst of the 7 categories the participant was in that day will constitute the primary outcome. The 7 categories are:

7. Death
6. End-organ failure
5. Life-threatening end-organ dysfunction
4. Serious end-organ dysfunction
3. Moderate end-organ dysfunction
2. Limiting symptoms due to COVID-19
1. No limiting symptoms due to COVID-19

[Appendix F](#) provides clinical definitions of each category. In addition to the overall summary odds ratio (OR) that will be estimated as described in Section 11.1, ORs will be estimated for the 6 dichotomized definitions of improvement that can be formulated from the categories of the ordinal outcome.

#### 4.1.1 Rationale for Primary Endpoint at Day 7

The goals of this study are to assess the safety, tolerability and efficacy of a single infusion of hVIG in preventing further progression and mortality related to COVID-19 when administered at the onset of clinical progression, with the aim of improving the long term outcome of the disease process. There is as yet no consensus on the optimal endpoint for determining clinical benefit from COVID-19 therapies, including the constituent elements of the endpoint and the timing of its assessment after randomization. Both may differ depending on the target population and the nature of the treatment studied.

The primary ordinal outcome captures the range of severity experienced by hospitalized patients with COVID 19, recognizing that end-organ manifestations in addition to pneumonia and ARDS are increasingly emerging as significant contributors to morbidity. The ordinal outcome includes 7 well-defined mutually exclusive categories that assess further progression of disease as well as recovery from COVID-19.

The ordinal outcome includes both pulmonary manifestations as assessed in prior COVID-19 trials and additional components representing key non-pulmonary outcomes; the latter are highlighted as “*extra-pulmonary*” in the guidance table ([Appendix F](#)). The primary endpoint will include both pulmonary and extra-pulmonary components, while the pulmonary manifestation scale only will be reported as a secondary endpoint.

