### 10.2.5 Protocol-specified exempt events

These events are listed in sections 4.1 and 4.2 and are collected systematically during study follow-up on eCRFs. These events will not be reported as Grade 3 or 4 AEs even if they occur at that severity grade. They also will not be reported as SAEs, even if they meet one or more of the criteria for seriousness, ***unless the investigator considered that there was a reasonable possibility that the study intervention caused the event.*** These events may occur during the initial hospitalization, lead to a re-admission, or occur in a later hospitalization during follow-up.

The following are **protocol-specified exempt events**:

- Death
- Stroke
- Meningitis
- Encephalitis
- Myelitis
- Myocardial infarction
- Myocarditis
- Pericarditis
- New onset of worsening of CHF (NYHA class 3 or 4)
- Arterial or deep venous thromboembolic events
- Respiratory failure defined as receipt of high flow nasal oxygen, noninvasive ventilation, or invasive ventilation
- Hypotension requiring vasopressor therapy
- Renal dysfunction requiring renal replacement therapy
- Hepatic decompensation
- Acute delirium
- Disseminated intravascular coagulation
- Microbiologically-proven severe infection (not including SARS-CoV-2)

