## APPENDIX F CLINICAL CATEGORICAL DEFINITIONS FOR ORDINAL OUTCOME

*Each participant is categorized in the highest applicable category.*

Ordinal Category	Categorical Description	Categorical Definition*
7	Death	Death
6	End-organ failure	Currently requiring invasive assisted ventilation, extracorporeal membrane oxygenation, mechanical circulatory support, vasopressor therapy or renal replacement therapy
5	Life-threatening end-organ dysfunction	Currently requiring non-invasive assisted ventilation or high-flow oxygen or Extra-pulmonary: Symptoms and signs of an acute stroke (NIHSS > 14)
4	Serious end-organ dysfunction	Currently requiring supplemental oxygen ( $\geq 4$ liters/min, or $\geq 4$ liters/min above premorbid requirements**) but not high-flow oxygen or Any of symptoms or signs of the following extra-pulmonary conditions: Stroke (NIH Stroke Scale/Score [NIHSS] $\leq 14$ ), meningitis, encephalitis, or myelitis, myocardial infarction, myocarditis, pericarditis, or New York Heart Association Class III or IV congestive heart failure, arterial or deep venous thrombosis including pulmonary embolism.
3	Moderate end-organ dysfunction	Requiring supplemental oxygen < 4 liters/min, or < 4 liters/min above premorbid requirements**
2	Limiting symptoms due to COVID-19	Symptomatic and currently unable to independently undertake usual activities
1	No limiting symptoms due to COVID-19	Can independently undertake usual activities with minimal or no symptoms

*\*Continued hospitalization or presence in a particular category of inpatient facility (e.g. intensive care or high dependency) is not used to divide these categories, as indication for continued hospitalization among recovering COVID patients is intrinsically subjective, in part determined by social and financial factors, and varies markedly across the globe.*

*\*\* Premorbid requirement refers to requirements prior to the development of COVID-19, for example in patients with chronic obstructive pulmonary disease, other chronic pulmonary diseases, or oxygen requirements related to altitude.*

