## 7.4 Secondary Outcomes

The protocol defines a number of secondary endpoints in addition to the two key endpoints described in the previous section. These analyses will be carried out for the final report. No adjustment for multiplicity for all the treatment comparisons for the secondary outcomes will be made; they are supportive to the primary endpoint analysis.

Selected secondary endpoints may also be analyzed for the interim monitoring report to help evaluate the safety and efficacy of hVIG.

*Multiple imputation will only be used for data missing on the primary endpoint; all secondary endpoints will use complete case.*

Below, the secondary outcomes from the protocol are cited, with a short description of the analysis methods. The secondary outcomes are grouped by analysis methods and are not listed in order of importance.

1. The primary ordinal outcome on Days 3, 5, 14 and 28.
2. Pulmonary only components of the primary outcome measure at Days 3, 5, 7, 14 and 28
3. Thrombotic components of the primary outcome measure (stroke, myocardial infarction, venous and arterial thrombosis or embolism, plus disseminated intravascular coagulation) at Days 3, 5, 7, 14, and 28.
4. Clinical organ dysfunction
5. The ordinal outcome similar to the one used in the ACCT trial of remdesivir will be used to compare treatment groups at Day 7. The ACCT ordinal outcome included 8 categories. We can only approximate the categories because data were not collected concerning hospitalization for infection-control reasons. It is similar to the ITAC primary ordinal outcome but

considers hospitalization status. The following 8 categories will be defined for this ordinal outcome:

- Not hospitalized, no limiting symptoms due to COVID-19
- Not hospitalized, limiting symptoms due to COVID-19, home oxygen requirement, or both
- Hospitalized, no limiting symptoms due to COVID-19, not requiring supplemental oxygen
- Hospitalized, limiting symptoms due to COVID-19, not requiring supplemental oxygen
- Hospitalized, requiring any supplemental oxygen
- Hospitalized, requiring non-invasive ventilation or use of high-flow oxygen devices.
- Hospitalized, requiring invasive mechanical ventilation or ECMO
- Death

6. Percentage in 2 most favorable categories at Day 7.
7. Hospitalization status at Days 14 and 28.

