## 10 Addendum to Statistical Analysis Plan for European Medicines Agency

During the review by EMA of INSIGHT 013 (ITAC), An International Multicenter, Adaptive, Randomized Double-Blind, Placebo-Controlled Trial of the Safety, Tolerability and Efficacy of Anti-Coronavirus Hyperimmune Intravenous Immunoglobulin for the Treatment of Adult Hospitalized Patients at Onset of Clinical Progression of COVID-19, it was requested that the data analysis plan be revised to make the 7-category pulmonary ordinal outcome at day 7 (a secondary endpoint) the primary endpoint for submissions to the EMA instead of the 7-category ordinal outcome specified in the protocol (see section 4 and Appendix F of the protocol) which also includes a range of organ dysfunction in addition to respiratory dysfunction. The protocol-defined primary endpoint would be a secondary endpoint for EMA submissions.

An addendum to Version 1.0 of the Statistical Analysis Plan was prepared on January 11, 2021 to address this request from the EMA. It is reproduced here for ease of reference.

The statistical data analysis plan based on the protocol, dated 25 September 2020, will not be changed as it reflects the protocol. For the EMA submission, this document will be submitted with the protocol and the statistical data analysis plan. Should the data analysis plan be modified before the end of the study, this document will be submitted with the updated statistical data analysis plan.

For the EMA submission, the ordinal outcome shown in the table at the end of this section will be used as the primary endpoint. Sample size assumptions, as stated in section 5.5 of the protocol, are not expected to differ for this outcome compared to those stated in the protocol for the primary endpoint. This assumption is supported by results from another trial, INSIGHT 014 (TICO), for which similar endpoints were used. A paper describing the findings from TICO at day 5 for both ordinal outcomes reported that only 2 of 311 participants were in different categories of the two ordinal outcomes (ACTIV-3/TICO LY-CoV555 Study Group, *N Engl J Med* 2020, doi: 10.1056/NEJMoa20331.30).

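### The only thrombosis-specific outcome is read as status on five separate days; a cumulative comparison through Days 7 and 28 should be added.

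*SAP*

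**What the plan says.** Protocol 3.1.2 raises the risk: "There is potentially a slight elevation in the risk of thrombosis with standard IVIG therapy". It then says how the trial will watch for it: "any thrombotic events will form part of the primary endpoint assessment and be monitored during interim safety analyses by the DSMB". Protocol 4.2 item 13 lists thrombotic outcomes among the measures of safety and tolerability.

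The dedicated outcome is protocol 4.2 item 10, which SAP 7.4 repeats as item 3 in these words: "Thrombotic components of the primary outcome measure (stroke, myocardial infarction, venous and arterial thrombosis or embolism, plus disseminated intravascular coagulation) at Days 3, 5". The list of days goes on to Days 7, 14 and 28. SAP 7.4 analyses items 1 to 8 by proportions in each arm, with an odds ratio from a cumulative or binary logistic model. Items 9 and 10 have Kaplan-Meier and Cox methods, and items 11 to 14 have competing-risk methods.

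The parent measure is status on a day. Protocol 4.1 says: "On Day 7, the worst of the 7 categories the participant was in that day will constitute the primary outcome". In Appendix F the thrombotic conditions require symptoms or signs and sit in category 4, except severe stroke in category 5. Appendix F also says: "Each participant is categorized in the highest applicable category".

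Protocol 10.2.5 makes thromboembolism, stroke, MI and DIC exempt events. "These events will not be reported as Grade 3 or 4 AEs even if they occur at that severity grade", and they are not SAEs either unless the investigator sees a reasonable possibility that the study intervention caused them.

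**The concern.** A harm that can occur on any day is measured by who shows it on five particular days. A listed day misses a thrombosis that has already resolved and one that has not yet begun. An event that starts and resolves, or starts and ends in death, between two listed days may appear on none of them.

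At stake is the ability to see an excess of thrombosis on hIVIG. Thrombosis is uncommon enough that every event matters, and it is largely taken out of routine AE reporting because it is collected as an endpoint. A reader of the final report would naturally look to item 3 for the answer. If item 3 holds only part of the events, a similar count in the two arms is weaker reassurance than it looks.

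**Working it through.** **1. The plan's own figures.** Neither document states a rate, effect size or power for thrombosis, so there is no figure to reproduce on this point. The power formula used in step 5 can be checked against SAP 1.4. With 579/2 = 289.5 per arm and two-sided alpha 0.05, it gives 0.80 for 13.6% versus 6.6% (SAP: 80%) and 0.45 for 13.6% versus 8.8% (SAP: 45%).

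**2. What the primary endpoint captures.** Protocol 3.1.2 says that "any thrombotic events will form part of the primary endpoint assessment". The Day 7 definition is narrower. A thrombosis must show symptoms or signs on Day 7. A category 4 thrombosis also cannot move a participant already in category 4 or above, where Table 1 expects 28.1% of the placebo group. A severe stroke (category 5) can still move a participant out of category 4. The two passages do not agree.

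**3. What item 3 captures, read as day status.** An embolism on Day 2 that is fatal on Day 5 is seen on Day 3. One that begins on Day 15 and is fatal on Day 20 falls between Days 14 and 28. An event on Day 8 whose signs have gone by Day 13 falls between Days 7 and 14. An event between listed days is missed only if it has resolved, or the participant has died or is unassessed, by the next one.

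**4. Share of events seen (assumed inputs).** Let onset be on day t = 0 to 28, with signs present for d days including the onset day. Listed day D sees the event if t ≤ D ≤ t + d − 1.

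Uniform onset gives 29 equally likely days:
- d = 1: 5/29 = 17% seen on at least one listed day
- d = 3: 13/29 = 45%
- d = 7: 22/29 = 76% (onset on Days 0–14 and 22–28)
- d = 14: 29/29 = 100%

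With front-loaded onset, weights exp(−t/7), the same durations give 22%, 63%, 92% and 100%.

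Each day is analysed separately. With d = 7 and uniform onset, the single-day shares are 4/29 = 14% on Day 3, 6/29 = 21% on Day 5, and 7/29 = 24% on each of Days 7, 14 and 28. With front-loaded onset, Day 7 sees 56% and Day 28 sees 3%.

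**5. Effect on precision (assumed rates).** Take cumulative risks p1 = 3% on placebo and p2 = 7% on hIVIG, with n = 289.5 per arm, and let share s of events be seen in both arms. The observed rates are then s·p1 and s·p2. Power = Φ[(difference − 1.96·SE0)/SE1], where SE0 uses the pooled rate and SE1 the separate rates.

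| s | Expected events | Power |
|---|---|---|
| 1.00 | 8.7 vs 20.3 | 0.60 |
| 0.75 | 6.5 vs 15.2 | 0.48 |
| 0.50 | 4.3 vs 10.1 | 0.34 |
| 0.25 | 2.2 vs 5.1 | 0.19 |

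The ratio of rates stays at 7/3 throughout. What falls is the number of events, and with it the precision.

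**6. Where thrombosis is counted cumulatively.**
- Protocol 4.2 item 12 counts new onset through Day 28, along with respiratory, renal, hepatic and infective events. SAP 7.4 makes this one binary composite at interim and a weighted score at the end.
- SAP 7.2 analyses exempt SAEs as one class. The exempt list in protocol 10.2.5 includes respiratory failure, renal replacement and severe infection.
- SAP 7.2 also breaks its composites down by system organ class. The protocol's own organ list puts MI under cardiac, stroke under neurological, and DIC and other thrombosis under hematological, so a grouping by organ divides thrombosis.

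None of these sets all thrombotic events side by side by arm.

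**The case against.** The strongest reply is that thrombosis is not neglected. The events are collected through Day 28. Protocol 3.1.2 places them under DSMB monitoring, and protocol 11.3 puts the section 4.2 safety outcomes into the DSMB summaries. A thrombosis considered related is reported as an SAE, within 24 hours if related to the investigational agent (10.2.6). Organ-dysfunction proportions could also be tabulated item by item. All of this stands. The plan does not, however, specify an item-level comparison, and the thrombosis line in item 12 excludes stroke, MI and DIC, which are listed separately.

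A second reply is that day status is inferred. Item 3 does not say whether a result at a given day means present that day or occurred by that day. It adds DIC, which Appendix F lacks, so it is not a pure subset of the scale. Nor does it say how a participant who has died is scored; the highest-category rule belongs to the seven-category scale. This also stands, and is a reason to define the item.

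Three stronger readings are tempting, and the documents do not support them:
- *Thromboses, above all fatal ones, disappear from the trial.* They do not: the events and deaths are collected, and a fatal case whose signs are present on a listed day counts on that day.
- *The comparison is biased toward no harm.* Equal loss in both arms leaves the ratio unchanged, as step 5 shows. Bias on the ratio scale would need different loss by arm, for which there is no evidence.
- *Thrombosis is almost invisible, since in a related trial "only 2 of 311 participants were in different categories of the two ordinal outcomes".* That is Day 5 disagreement between two scales in another trial. It is not a thrombosis rate and says nothing about item 3.

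**Conclusion.** The point holds in limited form. The only outcome devoted to a named risk of hIVIG is, on its natural reading, five separate day-status snapshots, and no cumulative thrombosis-specific comparison by arm is specified.

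The loss depends on how long signs last. If they last two weeks, the five days together miss nothing; if 7 days, they miss 8% to 24%; if 1 day, about 80%. Any one day sees less than the five together. Onset pattern, duration and event rates are all assumptions. Even with every event counted, power for 3% versus 7% is only 0.60, so a cumulative analysis improves the comparison without making it well powered.

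This is a cheap improvement to a safety analysis. It changes neither the primary analysis nor the sample size.

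**What to change.** In SAP 7.4 item 3 and SAP 7.2, add the cumulative incidence of first new thrombotic event (stroke, MI, venous or arterial thrombosis or embolism, DIC) through Day 7 and through Day 28, by arm. Count fatal thrombosis as an event and death from other causes as competing. Use the Gray and Aalen-Johansen methods that SAP 7.4 already gives for outcomes 11 to 14, and show event counts by type. This assumes that onset dates are recorded; if not, report the proportion with an event by each of the two days.

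Keep the five-day summaries as description. State whether they are day status or occurrence by that day, and how deaths are scored.

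Reconcile protocol 3.1.2 with the Day 7 status definition in 4.1 and Appendix F. Also reconcile protocol 9.1.2, which has ordinal assessments on Days 3 and 5 for all participants, with the Appendix B footnote, which gives outpatients only Days 7, 14 and 28. Item 3 is a complete-case analysis, so this affects its denominators.

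The cost is about one paragraph and one table, from events already collected, plus one more comparison without multiplicity adjustment, as for the other secondary outcomes. SAP 2.0 was prepared before unblinding, and the addition carries most weight if it is dated before unblinding too.
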